6.3.2.3. Definition of Toxicity Grades

Toxicity grades will only be derived for laboratory tests for which toxicity grades are available.

Toxicity grades will be determined as implemented in the attached table ([Appendix I](#)).

For elevations (H1 to H4), values under the threshold of H1 are reported as 'Grade 0'.

For elevations (L1 to L4), values above the threshold of L1 are reported as 'Grade 0'.

6.3.2.4. Definition of Non-Graded Abnormalities

For all laboratory tests provided by the laboratory, the position of the actual analysis values versus their normal ranges will be determined directly by using the position indicator provided in the database as provided by the lab, expressing the classes for these analysis values as low (L), normal (N) or high (H). L, N and H are further referred to as non-graded abnormalities.

6.3.2.5. Urinalysis Tests with Categorical Results

Results of urinalysis with qualitative results will be tabulated by time point. No toxicity grading or non-graded abnormalities will be derived for these tests.

6.3.2.6. Treatment-Emergent Principle

Toxicity Grades

A post-baseline toxicity grade 1, 2, 3 or 4 is defined as treatment-emergent when higher than the toxicity grade of the baseline result or when there is a change in direction (from H to L or from L to H). If the baseline result is missing, a post-baseline toxicity grade 1, 2, 3 or 4 will be considered as treatment-emergent.

Non-graded Abnormalities

A post-baseline non-graded abnormality class L or H is defined as treatment-emergent when it differs from the abnormality class of the baseline result. If the baseline result is missing, a post-baseline abnormality L or H will be considered as treatment-emergent.

6.3.2.7. Worst-Case Principle

Toxicity Grading

The worst-case post-baseline toxicity grade 0, 1, 2, 3 or 4 will be determined per subject, per laboratory test (and direction, increases and decreases) and for each analysis period, using all non-missing post-baseline records (including unscheduled and FU visits).

The worst-case toxicity grade is the highest toxicity grade corresponding to the highest laboratory test value (by direction, increases and decreases). In case of several equal highest post-baseline actual values, the earliest occurrence will be taken for the analyses and will be flagged in the listings.

- Grade 0: all post-baseline toxicity grades are classified as 0
- Grade 1: all post-baseline toxicity grades are classified as ≤ 1
- Grade 2: all post-baseline toxicity grades are classified as ≤ 2
- Grade 3: all post-baseline toxicity grades are classified as ≤ 3
- Grade 4: all post-baseline toxicity grades are classified as ≤ 4

If any record is missing, then the toxicity grade is considered as ‘missing’.

Non-graded Abnormalities

The following worst-case post-baseline abnormalities L, N or H will be determined per subject, per laboratory test and for each analysis period, using all non-missing post-baseline records (including unscheduled and FU visits):

- L = low: at least one post-baseline result is classified as L.
- N = normal: all post-baseline results are classified as N.
- H = high: at least one post-baseline result is classified as H.

If, for a subject, both L and H are reported, the subject will be counted twice in the table: once with a worst-case L and once with a worst-case H.

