4.3.6.2. Handling of Missing Result Data

No imputation will be done of missing result data unless otherwise specified. That is, an observed case (OC) analysis will be performed unless otherwise specified. Endpoints analyzed via mixed models for repeated measures (MMRM) handle missing data via the maximum-likelihood function.

For some binary endpoints, missing data will be handled using both an OC approach and non-responder imputation (NRI) as specified in [Section 6.2](#). NRI being the imputation of missing values by a non-response/non-remission.

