4.4.3. Calculation of Percentages

Frequencies and percentages will be generated for categorical parameters.

For event-type data (e.g. AEs), the denominator will be all subjects in the analysis set and analysis period. For other data (e.g. worst-case analysis of assessments), the denominator will be all subjects with (post-baseline) data for the parameter, in the analysis set and analysis window/period.

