6.3.2.9. Presentation of Results

No formal inferential statistics (p-values) will be derived.

Continuous laboratory tests¹⁶ including glucose, cholesterol, triglycerides, low-density lipoprotein (LDL), high-density lipoprotein (HDL) and fasted glucose, will be summarized by means of descriptive statistics (including 90% CI of the mean change) by laboratory test, treatment group and analysis window. Actual values, changes from baseline and percent change from baseline will be tabulated separately. Continuous values for metabolic markers will be summarized in the pharmacodynamic analysis section.

Profile line plots by subject of all actual observed values using relative day (ADY) will be presented by treatment group. Graphs of the mean (+- SE) actual values over time and of the mean (+- SE) change from baseline, and percent changes from baseline will be presented for all continuous laboratory parameters, with the exception of the metabolic markers. Also, line plots for subjects will be provided by treatment group.

The analysis of abnormalities will focus on assessments reported during the treatment period. Results reported before baseline will only be listed.

Non-graded abnormalities and toxicities grades of the actual values will be presented as shift tables of the worst-case abnormality/toxicity grade versus the baseline abnormality/toxicity

¹⁶ With the exception of the metabolic markers [fasted insulin, homeostatic model assessment of insulin resistance (HOMA-IR) and HbA1c] and inflammation marker hsCRP.

grade. The table will be created per laboratory test, treatment group and analysis period. The results of non-graded abnormalities and toxicities grades will be shown separately.

A frequency table of the number (percent) of subjects with treatment-emergent worst-case abnormalities/toxicity grade per laboratory test, treatment group and analysis period will be presented. The results of non-graded abnormalities and toxicities grades will be shown separately.

A frequency table of the number (percent) of subjects will be also provided for hepatotoxicity flags defined before. These abnormalities will be also flagged in the individual data laboratory listing.

Listing will be provided for the laboratory test along with flag for abnormality results. In addition, pregnancy result will be listed separately.

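### SAP 6.3.2.7 contradicts itself on missing records: read literally, one missing record turns an observed Grade 3 or 4 into a missing grade in the graded worst-case laboratory tables

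*SAP*

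**What the plan says.** The toxicity-grading part of SAP 6.3.2.7 opens by saying that the worst-case grade is determined per subject, laboratory test, direction and analysis period, "using all non-missing post-baseline records (including unscheduled and FU visits". It then defines the quantity as a maximum: "The worst-case toxicity grade is the highest toxicity grade corresponding to the highest laboratory test value (by direction, increases and decreases". A list of Grades 0 to 4 follows, and after it one unqualified sentence: "If any record is missing, then the toxicity grade is considered as ‘missing". No exception is made for a high grade already observed, and the term record is not defined.

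The rule beside it for non-graded abnormalities needs only one abnormal result ("H = high: at least one post-baseline result is classified as H") and has no missing-record clause.

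The general provisions point the same way as the opening sentence. SAP 4.3.6.2 sets an observed-case default: "No imputation will be done of missing result data unless otherwise specified". For worst-case tables, SAP 4.4.3 says that "the denominator will be all subjects with (post-baseline) data for the parameter"; complete data are not required.

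Under SAP 6.3.2.9 the worst-case grade is used in a shift table against baseline and in this output: "A frequency table of the number (percent) of subjects with treatment-emergent worst-case abnormalities/toxicity grade per laboratory test, treatment group and analysis period".

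**The concern.** A worst case is a maximum. A sample that is missing cannot lower a maximum that has already been seen. A rule that blanks the grade whenever a record is missing therefore discards information that is in hand, and in a safety table it discards it in the unsafe direction.

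Elsewhere the SAP resolves missing safety information conservatively: a missing baseline makes any post-baseline Grade 1 to 4 treatment-emergent (6.3.2.6), and a missing causality assessment counts as related (6.3.1.4). The sentence in 6.3.2.7 does the opposite.

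At stake are the two tables that summarize laboratory toxicity by grade. With 15 and 10 subjects planned per arm, one severe grade is a visible part of the result. Two programmers could each defend a different table from the same SAP. The graded and non-graded tables could also disagree for the same subject and test, with H in one and missing in the other.

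**Working it through.** **Step 1. The provisions applied to one subject.** Take post-baseline grades 0, 3, (no result), 1 for an elevation.

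| Provision | Place | Result |
|---|---|---|
| Use the non-missing records | SAP 6.3.2.7, opening | Grade 3 |
| Worst case is the highest grade | SAP 6.3.2.7, definition | Grade 3 |
| Any missing record | SAP 6.3.2.7, after the grade list | missing |
| Non-graded rule, one H is enough | SAP 6.3.2.7 | H, if the value is above the normal range |
| Observed-case default | SAP 4.3.6.2 | Grade 3 |
| Denominator | SAP 4.4.3 | subject is counted |

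Only one provision gives a missing grade.

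**Step 2. Effect on a reported rate.** The subject has post-baseline data and so stays in the denominator, but leaves the Grade 3 numerator. If this is the only Grade 3 in its arm:

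- GLPG3970: 1/15 = 6.7% becomes 0/15 = 0%.
- Placebo: 1/10 = 10% becomes 0/10 = 0%.

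**Step 3. How many subjects could have a missing record.** The plan's own figure first: 20 completers at 20% dropout need 20 / (1 − 0.20) = 25 randomized, which matches SAP 2.6. Planned dropouts are 0.20 × 25 = 5, or 0.20 × 15 = 3 on GLPG3970 and 0.20 × 10 = 2 on placebo. The schedule (SAP 2.5) has 4 post-baseline safety blood draws for a subject who completes: Visits 3, 4, 5 and FU.

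Let m be the chance that a draw gives no result. The documents give no value, so 1% to 10% is assumed, with draws independent.

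- Narrow reading (visits not held after dropout are not records): share = 1 − (1 − m)^4
- Broad reading (every dropout has a missing record): share = 0.20 + 0.80 × [1 − (1 − m)^4]

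| Assumed m | Narrow share | Broad share | Broad, of 25 |
|---|---|---|---|
| 0 | 0% | 20% | 5 |
| 1% | 4% | 23% | 5.8 |
| 2% | 8% | 26% | 6.6 |
| 5% | 19% | 35% | 8.7 |
| 10% | 34% | 48% | 11.9 |

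These are subjects with any missing record, not severe grades lost. The documents give no expected rate of Grade 3 or 4, so the second number cannot be derived. If missingness were unrelated to grade, the share in the table would be the chance that any one observed Grade 3 or 4 is blanked. Under the non-missing rule that chance is 0 at every m.

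**Step 4. A side effect of the undefined term.** SAP 6.3.2.2 derives no grade for glucose or triglycerides from non-fasted samples, while protocol 8.1 requires fasting only at Visits 1, 3, 5 and ED. If an ungraded record counts as missing, a non-fasted Visit 4 or FU sample would blank the grade for those two tests.

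**The case against.** Several points against the concern have force.

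- **The sentence may not mean what it says.** It refers to the toxicity grade, not the worst-case grade, so it could be a record-level statement that a missing record has no grade. The author may also have meant that all records are missing. Both are plausible, and both agree with the rest of the SAP. But the sentence closes the list that defines the worst-case grade, and nothing on the page limits it. This supports clarifying the text; it does not remove the contradiction.
- **With a missing record the true maximum is unknown.** The list defines each grade by a statement about all post-baseline grades, which cannot be fully verified when one is absent. That is a fair caution about Grade 0. It does not justify dropping an observed Grade 3, which is a lower bound, or an observed Grade 4, which is the top of the scale.
- **The result survives elsewhere.** A reader might infer that a severe result vanishes from the report. It does not. SAP 6.3.2.9 provides a "Listing will be provided for the laboratory test along with flag for abnormality results", along with plots of all observed values by subject. The non-graded tables keep any out-of-range value. Liver tests have their own table of multiples of the upper limit (6.3.2.8), with no missing clause. SAP Appendix I asks for treatment-emergent results of grade 2 or above to be described in the study report, and 6.3.2.6 defines treatment-emergent without this sentence. Protocol 11.1.5 requires abnormalities that lead to interruption or discontinuation to be recorded as adverse events. All of this stands. It leaves the two graded tables, and most graded tests have no separate table of the liver kind.
- **Dropouts need not lose their grade.** Subjects who discontinue treatment are asked for ED and FU visits, both with safety bloods, and a visit never held may create no record. Protocol 8.1.1 also allows one resampling of a safety test for technical reasons. So 5 of 25 is an upper figure for dropout, not an expected one.
- **Selective loss is not shown.** A reader might infer that severe grades are lost preferentially, and more in the arm with more toxicity. It is plausible that subjects stopped for a laboratory abnormality have more missing later samples. The documents do not establish it, and the ED and FU requests and close liver monitoring work against it.

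**Conclusion.** The contradiction in SAP 6.3.2.7 is real, and it changes the result for any subject with an observed toxicity and a missing record. Programmed literally, the last sentence biases the Grade 3 and 4 rates downward in the graded worst-case shift table and the treatment-emergent frequency table; each loss costs an arm one subject in 15 or one in 10.

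The reach is limited to those two tables. Safety is analyzed descriptively and the primary endpoint is untouched.

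The number of subjects exposed is uncertain. It rests on what a record is, on missed-sample rates that the documents do not give, and on independence between draws. The firmest figure is up to 5 of 25 from the plan's own 20% dropout, on the broad reading. The higher figures in the table depend on assumed rates and should not be quoted as expected losses. This is a point that should be fixed; it does not call the trial's main conclusions into question.

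**What to change.** Replace the sentence with: *Missing records are ignored; the worst-case grade is the highest grade among the non-missing post-baseline records, and is missing only if the subject has no non-missing post-baseline record for that test.*

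In the same place, state what counts as a record, and say that samples left ungraded under 6.3.2.2 (non-fasted glucose and triglycerides) are ignored in the same way. If the original intent was that all records are missing, this wording expresses it.

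The cost is one or two sentences in the SAP and a check of the matching program. No new data or assessments are needed.

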6.3.2.8. Hepatotoxicity

Hepatotoxicity will be investigated by tabulating the aspartate aminotransferase (AST) and alanine aminotransferase (ALT) values categorized as >3 , >5 , >10 and >20 times their upper limit of normal (per analyte and over both analytes combined), ALP categorized as > 1.5 times the upper limit and total bilirubin as > 2 times the upper limit of normal. Elevations of AT (AST or ALT) > 3 times their upper limits accompanied by elevated total bilirubin ($>1.5 \times \text{ULN}$, $>2 \times \text{ULN}$) on the same day will also be tabulated.

To assess the potential of the drug to cause severe liver damage, possible Hy's Law cases will be identified. These subjects are defined as having any elevated AT (AST or ALT) of $>3 \times \text{ULN}$, ALP $<2 \times \text{ULN}$, and associated with an increase in total bilirubin $>2 \times \text{ULN}$ on the same day.

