8. CLINICAL STUDY ASSESSMENTS

Every effort should be made to ensure that CSP-required tests and procedures are completed as described in the Schedule of Activities (see Section 8.11). To avoid inter-observer variability, every effort should be made to ensure that all safety and efficacy evaluations are completed by the same individual who made the initial baseline determinations. In case study assessments are not performed for reasons related to SARS-CoV-2 pandemic restrictions, this should be documented in the medical records and e-CRF.

In case a randomized subject is not available to attend a scheduled study visit on site due to of SARS-CoV-2 travel restrictions, a phone call or a televisit may be conducted instead. It is strongly recommended to conduct planned study assessments for the applicable visit as per protocol as much as possible. If possible and if local regulations allow and the subject agrees, trained study staff or trained personnel are encouraged to collect study assessments at the study subjects' home or a local facility if social distancing and hygiene rules can be applied.

Only staff trained in conducting the protocol planned assessments are authorized to perform home or local facility visit assessments and the alternative arrangements need to be adequately documented. Direct to patient shipments are possible if needed. Subjects presenting with signs and symptoms of infection, including SARS-CoV-2 infection should immediately contact the site investigator, who should inform the sponsor's medical responsible as soon as possible, and SARS-CoV-2 testing should be performed.

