11.1.4. Adverse Events of Special Interest

Not applicable.

11.1.5. Clinical Laboratory Abnormalities and Other Abnormal Assessments as Adverse Events or Serious Adverse Events

Laboratory abnormalities without clinical significance based on the investigator's judgment are not considered AEs or SAEs. However, laboratory abnormalities (e.g. clinical chemistry, hematology, and urinalysis) or other abnormal (clinical study-specific) assessments (e.g. ECG, radiography, vital signs) that require medical or surgical intervention, are associated with signs and/or symptoms, and/or lead to IP interruption, modification or discontinuation must be recorded as an AE or SAE if they meet the definition as described in Sections 11.1.1 and 11.1.2, respectively. If the laboratory abnormality is part of a syndrome, the syndrome or diagnosis is to be reported (e.g. anemia instead of decreased hemoglobin).

The following liver enzyme elevations should be reported as SAEs:

- AST or ALT ≥ 8 xULN.
- AST or ALT ≥ 3 xULN with signs of liver damage (total bilirubin >2 xULN OR international normalized ratio >1.5 , and/or with the appearance of fatigue, nausea, vomiting, right upper quadrant pain or tenderness, fever, rash and/or eosinophilia [$>5\%$]).

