Appendix 8: Algorithm for Elevated Liver Function Tests

	AST or ALT increase to				
Value Range	$\geq 1.5x$ to $3x$ ULN	$\geq 3x$ to $<5x$ ULN	$\geq 5x$ to $<8x$ ULN	$\geq 3x$ ULN with signs of liver damage ¹	$\geq 8x$ ULN
IP Action	Continue as planned	Reduce or interrupt IP for at least 2 weeks	Interrupt IP for at least 2 weeks Close observation ²	Discontinue IP ²	Discontinue IP ²
		Close observation ²			
After at least 2 weeks	AST and ALT $<3x$ ULN	AST or ALT $\geq 3x$ ULN			
	Weekly LFTs for the first 2 weeks (biweekly for the following weeks, or more frequently at investigator's discretion)	Discontinue IP Report SAE and complete liver event page for any of abnormalities listed below ³ : 
 - AST/ALT increase $\geq 8x$ULN - AST/ALT increase $\geq 3x$ULN with signs of liver damage¹ 			

¹ Signs of liver damage:

- total bilirubin $\geq 2.0x$ ULN OR international normalized ratio >1.5 , and/or
- symptoms: appearance of fatigue, nausea, vomiting, right upper abdominal quadrant pain or tenderness, fever, rash and/or eosinophilia ($>5\%$)

² Close observation recommendations:

- Monitor 2 to 3 times per week all of the following parameters: ALT, AST, ALP, total bilirubin, eosinophils, INR. If local regulations allow, home visits can be performed if subjects cannot come to the clinical study center.
- Frequency of retesting can be reduced to once a week or less if abnormalities stabilize or the IP has been discontinued; however, monitoring might still be needed more frequently taking into consideration the standard of care and/or changes to this.
- Based upon investigator's discretion gastroenterology or hepatology consultations, additional serology testing, imaging, and pathology assessments may be required.
- Re-query history of symptoms, prior and concurrent diseases, concomitant medication and non-prescription medicines, herbal, dietary supplements, alcohol use, recreational drug use, special diets.
- Rule out all of the following: acute viral hepatitis, autoimmune hepatitis, alcoholic hepatitis, non-alcoholic fatty hepatitis, hypoxic/ischemic hepatitis, biliary tract disease, and cholestasis.
- Re-query exposure to environmental chemical agents.

³ The following steps should be followed:

- The site should immediately contact the subject and require the subject to discontinue IP immediately. The subject should be asked to return to the site within a 48-hour window from awareness of the result.

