6.3.2. Laboratory Safety

6.3.2.1. Available Data

Laboratory tests scheduled are described in the protocol section 8.5.2. In addition, the derived laboratory tests described in Section [6.3.2.2](#) will be added.

The statistical analyses will only present results in Standard International (SI) standardized units. Other units will not be presented.

Only data provided by the central laboratory along with corrected calcium (mmol/L) will be used in tables and figures. Results from local labs will be listed only.

The parameter (hs)CRP will not be presented in this laboratory section of the analysis, but presented in the efficacy part.

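### The same-day condition in SAP 6.3.2.8 can leave a subject whose bilirubin rises after the transaminases have fallen out of the combined-elevation and possible Hy's Law counts

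*SAP*

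**What the plan says.** SAP 6.3.2.8 tabulates AST and ALT, per analyte and over both, in classes above 3 and above 5, then ">10 and >20 times their upper limit of normal". It has single-analyte rows for ALP above 1.5 x ULN and total bilirubin above 2 x ULN. AST or ALT above 3 x ULN with bilirubin above 1.5 x or above 2 x ULN "on the same day will also be tabulated". In addition, "possible Hy's Law cases will be identified": AST or ALT above 3 x ULN, ALP below 2 x ULN and bilirubin above 2 x ULN, again on one day.

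SAP 6.3.2.1 restricts laboratory tables and figures to central-laboratory data plus corrected calcium: "Results from local labs will be listed only". SAP 6.3.2.9 puts the hepatotoxicity flags into a frequency table and the laboratory listing, and states "No formal inferential statistics (p-values) will be derived".

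Protocol 11.1.5 says "The following liver enzyme elevations should be reported as SAEs": AST or ALT at or above 8 x ULN, or at or above 3 x ULN with signs of liver damage (bilirubin, INR, symptoms or eosinophilia). Section 6.4 and Appendix 8 use the same structure. None of them says that the signs must fall on the day of the transaminase elevation. For close observation, Appendix 8 asks sites to "Monitor 2 to 3 times per week all of the following parameters: ALT, AST, ALP, total bilirubin, eosinophils, INR".

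**The concern.** Under Appendix 8, a subject whose transaminases rise enough has IP interrupted or stopped and is then sampled several times a week. In such a series the transaminases can fall while bilirubin is still rising. Measuring the analytes together does not help when their peaks fall on different days. If bilirubin first passes 2 x ULN after AST and ALT have dropped to 3 x ULN or below, no single day meets the SAP definition.

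The laboratory listing does not repair this, because its flags are the ones defined in 6.3.2.8. The subject would carry separate transaminase and bilirubin flags, but nothing would mark the pair as a possible Hy's Law case. This is the first study of GLPG3970 in subjects with RA (Protocol 5.5), on background MTX, so a zero in that row will be read as reassurance.

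**Working it through.** The documents give no figure to reproduce here. The check applies the written rules to hypothetical subjects. All laboratory values below are assumptions, in multiples of ULN.

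**Rules applied**
- Protocol 11.1.5: maximum AST/ALT >= 8, or maximum AST/ALT >= 3 with bilirubin > 2 or another sign of liver damage. No day condition is applied, because none is written.
- SAP combined: on one day, central data, AST/ALT > 3 with bilirubin > 1.5 (first class) or > 2 (second class).
- SAP Hy's Law: on one day, central data, AST/ALT > 3, bilirubin > 2, ALP < 2.
- SAP Appendix I grade H4, per analyte: > 8.0.

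| Case (ALP 1.0 throughout) | Protocol liver SAE | Single-analyte rows | Combined | Hy's Law |
|---|---|---|---|---|
| A. Day 15 ALT 6, bilirubin 1.0; Day 18 ALT 2.8, bilirubin 2.5; central | yes | >3, >5, bilirubin >2 | no | no |
| B. ALT 6, bilirubin 2.5, same day, local laboratory only | yes | none | no | no |
| C. ALT 9, bilirubin 1.0, central | yes | >3, >5 (and H4) | no | no |
| D. ALT 9, bilirubin 2.5, same day, central | yes | >3, >5, bilirubin >2 (and H4) | yes | yes |
| E. ALT exactly 8.0, bilirubin 1.0, central | yes | >3, >5 (not H4) | no | no |
| F. ALT 4, bilirubin 2.5, same day, central | yes | >3, bilirubin >2 | yes | yes |

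**Reading the table**
- Case A is the point. On Day 15 bilirubin is 1.0, below both combined classes. On Day 18 ALT is 2.8, below the entry level of 3. Neither day qualifies.
- Case B is lost through the central-only rule, not the day rule.
- Case C is outside the Hy's Law and combined counts because bilirubin is normal. Case D, also at 9 x ULN, is counted. So the absence of an 8 x row has no bearing on those counts.
- Case E shows a small mismatch: the protocol includes 8.0 exactly, and H4 excludes it.

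**Size.** One case A subject among the 15 planned on active drug is 1/15 = 6.7%; the Hy's Law row would show 0/15.

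**A related inconsistency.** The bilirubin criterion for liver damage is >= 2.0 x ULN in the discontinuation list of Protocol 6.4 and in Appendix 8, >= 1.5 x ULN in the second list of 6.4, and > 2 x ULN in 11.1.5. These passages must be reconciled. Case A does not depend on the outcome, since 2.5 exceeds all of them.

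**The case against.** The strongest reply is that little is lost. In a 25-subject trial, a case A subject remains in the AST/ALT >3 and >5 rows, the bilirubin row, the laboratory listing and the by-subject profile plots. If the event is reported as an SAE, it is also in the SAE listing and, when treatment-emergent, in the serious TEAE table (SAP 6.3.1.8). An internal committee sees unblinded safety data. All of this stands, and it limits the harm to misclassification within the liver analysis.

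Second, the protocol is silent on timing and could be read as requiring concurrent signs. That also stands: a reader might infer an any-time rule, but the documents do not establish one. The silence is a reason to define the window in the SAP.

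Third, Protocol 8.9 sends routine safety samples to a central laboratory, and the pandemic provision to "collect study assessments at the study subjects' home or a local facility" concerns where assessments are done, not where blood is analysed. A reader might infer that urgent liver work-ups will use local laboratories, but no passage says so. Still, SAP 6.3.2.1 itself provides for local results, and 8.9 does not expressly cover extra liver follow-up samples.

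Fourth, a Hy's Law screen is narrower than the protocol's SAE rule by design. SAEs based on symptoms, INR or isolated transaminases at or above 8 x ULN are not meant to be in it, and their absence is no fault.

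Finally, any window wider than one day is a choice and may add false positives. That is true. The window proposed here is bounded by the SAP's treatment analysis period, which ends at last contact; the follow-up visit is scheduled for Day 57 ± 3.

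**Conclusion.** The point holds in a limited form and is worth fixing because the fix is cheap. A subject whose bilirubin exceeds 2 x ULN only after AST and ALT have fallen to 3 x ULN or below is not counted or flagged as a possible Hy's Law case. If bilirubin was also no higher than 1.5 x ULN while the transaminases were above 3 x ULN, the subject is absent from the combined rows too. With bilirubin at, say, 1.6 x ULN on the day of ALT 6 x ULN, the subject would enter the combined >1.5 x ULN row and be missed only in the >2 x row and the Hy's Law count.

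The conclusion rests on reading the protocol's liver criteria without a day condition and on an assumed time course. The documents give no basis for estimating how often that course, or a local-only result, would occur.

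Two stronger readings are not supported. The case would not be missing from the trial's reporting as a whole. Nor does the lack of an 8 x ULN row in 6.3.2.8 remove anyone from the combined or Hy's Law counts: both start above 3 x ULN, and Appendix I grade H4 already tabulates values above 8.0 x ULN per analyte.

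**What to change.** In SAP 6.3.2.8:

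1. Keep the same-day rows. Add a row and a listing flag for total bilirubin > 2 x ULN on or after the day of AST/ALT > 3 x ULN within the treatment analysis period, with ALP < 2 x ULN at the transaminase elevation. Show same-day cases as a subset.
2. For these liver flags only, make an exception to SAP 6.3.2.1 and use any local-laboratory AST, ALT, ALP and total bilirubin, each divided by its own laboratory's ULN.
3. As a separate, minor alignment, add a >= 8 x ULN row over AST and ALT combined. Appendix I H4 is per analyte and uses a strict inequality where the protocol includes the boundary.

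The cost is SAP wording and minor programming, plus local reference limits in the data for any local result. No clinical rule, sample or visit changes. The downside is that a non-concurrent flag may pick up a case with another explanation; a short narrative settles that.
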